#### **10.7** Missing Data and Dropouts

The primary analysis will be performed in the group of individuals who initiate the evaluation period. Minimal loss is anticipated between randomization and this time point given the short time period. Intent-to-treat analysis with all cases will be performed assuming both the maximally pessimistic situation (all treated use daily, all control use never) and baseline use levels for these early withdrawals. The primary endpoint score imputes dropouts during the evaluation period to have use rates equal to that observed through the period prior to dropout. The TES will be used as a secondary analysis to assist with evaluating this effect. Note that in the design simulations, the TES 12-day analysis was observed to be less powerful than the analysis of the selected primary endpoint. But design assumptions did not assume interactions with treatment for either underreporting or withdrawal events.

#### **10.8** Demographic and Baseline Characteristics

Baseline demographic and clinical variables will be summarized for each arm of the study. Descriptive summaries of the distribution of continuous baseline variables will be presented with percentiles (median, 25th and 75th percentiles), and with mean and standard deviation. Categorical variables will be summarized in terms of frequencies and percentages. Since randomization is expected to produce balance at baseline between the three arms of the trial, statistical comparisons of treatment groups with respect to baseline characteristics should be

more informal. In case differences between treatments arms are suspected, statistical testing will be performed. For comparisons of treatment groups with respect to continuous baseline variables we will use the two sample Wilcoxon test. Group comparisons with respect to discrete baseline variables will use the chi-square test or Fisher's Exact Test as appropriate.

#### 10.9 Safety Analysis

Adverse events (AEs), including serious adverse events (SAEs), will be summarized by body system and preferred term using MedDRA (The Medical Dictionary for Regulatory Activities). Adverse events will be presented in two ways: (1) the number and proportion of participants experiencing at least one incidence of each event will be presented overall and by treatment group; and (2) a table displaying the total number of each event will be given overall and by treatment group. Listings of serious adverse events will be given, sorted by treatment, body system, and preferred term. Detail in these listings will include severity, relationship to study drug, and action taken as available. Treatment arm differences will be monitored by the DSMB.

# 11.0 **REGULATORY COMPLIANCE AND SAFETY MONITORING**

# **11.1** Regulatory Compliance

This study will be conducted in accordance with the current version of the protocol, in accordance with the ethical principles outlined in the Declaration of Helsinki, consistent with the International Conference on Harmonization Good Clinical Practice (GCP) Guidelines, and all other applicable regulatory requirements. An Operations Manual will be provided as a reference guide and study quality management tool.

# **11.2** Institutional Review Board Approval

Prior to initiating the study, site investigators will obtain written local IRB approval to conduct the study at their respective site. Should changes to the study protocol become necessary, protocol amendments will be submitted in writing by the investigators for IRB approval prior to implementation. In addition, IRBs will approve all consent forms, recruitment materials, and any materials (e.g., CBT Manual) given to the participant. Annual reports and progress reports will be submitted to the IRBs annually or at a frequency requested by each IRB. The lead investigator is responsible for maintaining in his research files copies of all performance site(s) current IRB/IEC approval notice(s), IRB-approved consent document(s), including approval for all protocol modifications. These materials must be received by the lead investigator prior to the initiation of research activities at a given site, and must be available at any time for audit.

# **11.3** Research Advisory Panel of California (California sites only)

Prior to initiating the study, the sponsor will obtain written approval from the Research Advisory Panel of California (RAP-C). Any planned research project to be conducted in California requiring the use of a Schedule I or Schedule II Controlled Substance as its main study drug as well as research for the treatment of controlled substance addiction or abuse utilizing any drug, scheduled or not (SAT) must be submitted to RAP-C for review and approval prior to study startup. Study approval is based on review of the study protocol, consent form, and other pertinent study documents. Yearly reports will be provided to the RAP-C in order to obtain continuing study approval.

# **11.4 Informed Consent**

All potential candidates for the study will be given a current local IRB-approved copy of the Informed Consent Form to read in English. Appropriately qualified and trained study personnel will explain all aspects of the study in lay language and answer all of the study candidate's questions. Participants who remain interested after receiving an explanation of the study will be given a short quiz to test his/her understanding of the project, the purpose and procedures involved, and the voluntary nature of his/her participation. Those who cannot successfully answer quiz items will have the study re-explained by research staff with a focus on aspects they did not understand. Anyone who cannot demonstrate appropriate understanding of the study will be ineligible to participate and will be assisted in finding other treatment resources. Those who demonstrate understanding of the study and voluntarily agree to participate will be asked to sign the informed consent form. Participants will not be administered any assessments or study procedures prior to signing informed consent.

The informed consent process is a means of providing study information to each prospective participant and allows for an informed decision about participation in the study. The informed consent form must be updated or revised whenever important new safety information is available, or whenever the protocol is amended in a way that may affect a study participant's

participation in the trial. Each study site must have the study informed consent approved by their local IRB(s). The site must maintain the original signed informed consent for every participant in a locked, secure location that is in compliance with their local IRB and institutional policies and that is accessible for quality assurance review and regulatory compliance. Every study participant should be given a copy of the signed consent form to keep for reference. Individuals who refuse to participate or who withdraw from the study will be treated without prejudice.

# 11.5 Drug Accountability

Upon receipt, the investigator, pharmacist, or authorized designee at each site is responsible for taking inventory of the investigational agents. A record of this inventory must be kept and usage must be documented. Any unused or expired investigational agent shall be accounted for.

# **11.6** Quality Assurance and Safety Monitoring

Research oversight bodies at all levels require assurance that the protection of the rights and welfare of study participants be a vigilant process conducted by the research team and by the sponsors of the research. Therefore, in addition to the data and safety monitoring procedures described in the preceding paragraphs, additional safety monitoring through the Data and Safety Monitoring Board will be conducted regularly throughout the duration of the study.

# **11.7** Data and Safety Monitoring Board (DSMB)

This study will utilize the CTN DSMB to oversee ongoing trial progress. The purpose of this board is to determine whether risks emerge during the conduct of the trial that make continuation unethical (e.g., clear and significant superiority of one condition over another). This process is intended to assure the IRBs, the sponsor, and investigators that participants are provided with an accurate and ongoing risk evaluation when participating in CTN research trials. Safety monitoring begins with the initial review of the protocol during the study development process. If serious or unexpected adverse events occur during the trial, the site medical clinican reports these occurrences within the specified time frames to the IRBs, NIDA, RAP-C (in California sites), and the FDA as required. The DSMB will meet twice annually.

#### **11.8 Medical Monitor**

A NIDA-assigned Medical Safety Monitor will be responsible for overseeing safety and for evaluating all Adverse Events (AEs). He/She will review all Serious Adverse Events (SAEs) within five days of their occurrence and all other Adverse Events on a regular basis. It is the responsibility of the site principal investigator to provide this information to the medical safety monitor. It is also the site principal investigators' responsibility to inform the IRBs per local IRB guidelines.

#### **11.9** Quality Assurance Monitor

The monitoring of the study site will be conducted on a regular basis using a combination of NIDA-contracted monitors and local quality assurance monitors. Investigators will host periodic visits by NIDA contract monitors and local QA monitors. The purpose of these visits is to encourage and assess compliance with GCP requirements and to document the integrity of the trial progress.

NIDA contract monitors will assure that submitted data are accurate and in agreement with source documentation and will also review regulatory/essential documents such as correspondence with the IRB. Areas of particular concern will be participant informed consent, protocol adherence, safety monitoring, IRB reviews and approvals, regulatory documents,

participant records, study drug accountability, and principal investigator supervision and involvement in the trial. Reports will be prepared following the visit and forwarded to the site principal investigator, the lead investigator and NIDA.

Qualified Node personnel (Node QA monitors) will provide site management for each site during the trial. This will take place as specified by the local protocol team, Node PI or lead team and will occur as often as needed to help prevent, detect, and correct problems at the study sites. Node staff will ensure site staff is trained and able to conduct the protocol appropriately and that study procedures are properly followed. If the node staff's review of study documentation indicates that additional training of study personnel is needed, node staff will undertake or arrange for that training. Details of the contract monitoring, node QA, and data monitoring are found in the study QA monitoring plan.

# 11.10 Statement of Compliance

This trial will be conducted in compliance with the appropriate protocol, current Good Clinical Practice (GCP), the principles of the Declaration of Helsinki, and all other applicable regulatory requirements. Participating sites must obtain written approval of the study protocol, consent form, other supporting documents, and any advertising for participant recruitment from their local institutional review board (IRB) in order to participate in the study. Prior to study initiation, the protocol and the informed consent documents will be reviewed and approved by an appropriate Ethics Review Committee (ERC) or IRB. Any amendments to the protocol or consent materials must be approved before they are implemented. Annual progress reports and local Serious Adverse Event (SAE) reports will be submitted to each IRB, according to its usual procedures.

# 11.11 Confidentiality

By signing the protocol signature page the investigator affirms that information furnished to the investigator by NIDA will be maintained in confidence and such information will be divulged to the IRB, Ethical Review Committee, or similar expert committee; affiliated institution; and employees only under an appropriate understanding of confidentiality with such board or committee, affiliated institution and employees. The lead investigator will obtain a federal Certificate of Confidentiality (CoC), protecting participants against disclosure of sensitive information (e.g., drug use), and will distribute it to all sites when received. The Department of Health and Human Services (HHS) office that issues the CoC will be advised of changes in the CoC application information. Participating CTP sites will be notified if CoC revision is necessary.

Participant records will be kept confidential by the use of study codes for identifying participants on CRFs, secure separate storage of any documents that have participant identifiers, and secure computing procedures for entering and transferring electronic data.

# **11.12** Health Insurance Portability Accountability Act (HIPAA)

Study sites may be required by their institutions to obtain authorization from participants for use of protected health information. Sites will be responsible for communicating with their IRBs or Privacy Boards and obtaining the appropriate approvals or waivers to be in regulatory compliance.

#### 11.13 Investigator Assurances

Each community treatment program site (CTP) must file (or have previously filed) a Federal Wide Assurance (FWA) with the HHS Office for Human Research Protection setting forth the commitment of the organization to establish appropriate policies and procedures for the

protection of human research subjects, with documentation sent to NIDA or its designee. Research covered by these regulations cannot proceed in any manner prior to NIDA receipt of certification that the research has been reviewed and approved by the IRB provided for in the assurance (45 CFR 46.103(b) and (f)). Prior to initiating the study, the principal investigator and sub-investigators at each study site will sign a protocol signature page, providing assurances that the study will be performed according to the standards stipulated therein.

#### 11.14 Financial Disclosure

All investigators will comply with the requirements of 42 CFR Part 50, Subpart F to ensure that the design, conduct, and reporting of the research will not be biased by any conflicting financial interest. It is the responsibility of the investigator to maintain appropriate disclosure to their individual institution according to their requirements.

# 11.15 DEA Registration

The sponsor or the sponsor representative must ensure that the DEA requirements, including registration, inspection, and certification, as applicable, are met. In order to receive shipments of study drug, sites must have a DEA registration (facility research registration or a practitioner registration) that has the address where study drug will be shipped on the registration. Additionally, dispensing any controlled substance requires a DEA registration unless exempt by federal or state law or pursuant to CFR Sections 1301.22-1301.26.

#### 11.16 Inclusion of Women and Minorities

A diverse group of study sites will be involved so that these sites can attract a diverse study population. If difficulty is encountered in recruiting an adequate number of women and/or minorities, the difficulties involved in recruitment will be discussed in national conference calls and/or face-to-face meetings, encouraging such strategies as linkages with medical sites and or treatment programs that serve a large number of women or minorities, advertising in newspapers or radio stations with a high female or minority readership/listening audience, etc.

# 11.17 Description of Plans to Conduct Valid Analyses of Study Results by Gender and Race/Ethnicity

The association between specific demographic characteristics and treatment outcome will be studied. The demographic characteristics of potential importance include: age, gender, race, and ethnicity.

#### **11.18 IND Requirements**

An IND application that was submitted for this study was reviewed, put into effect and given an IND number of 110,824 by the FDA. Going forward, any amendments to this clinical trial submitted to the FDA for review, will reflect awareness of and compliance with U.S Code of Federal Regulations 45 CFR 46 and it's subparts as well as the International Conference on Harmonization, Good Clinical Practice (ICH E6). This IND study will also be conducted in accordance with all applicable FDA regulations and will comply with all applicable laws and regulations at clinical research sites.

#### 11.19 Regulatory Files

The regulatory files should contain all required regulatory documents, study-specific documents, and all important communications. Regulatory files will be checked at each participating site for

regulatory document compliance prior to study initiation, throughout the study, as well as at study closure.

#### **11.20** Records Retention and Requirements

Research records for all study participants (e.g., case report forms, source documents, signed consent forms, and regulatory files) are to be maintained by the investigator in a secure location for a minimum of 3 years after the study is completed and closed. These records are also to be maintained in compliance with local IRB, State and Federal requirements, whichever is longest. The sponsor and lead investigator must be notified in writing and acknowledgment must be received by the site prior to the destruction or relocation of research records.

# 11.21 Audits

The Sponsor has an obligation to ensure that this trial is conducted according to good research practice guidelines and may perform quality assurance audits for protocol compliance. The Lead Investigator and authorized staff from the Pacific Region Node; the National Institute on Drug Abuse Clinical Trials Network (NIDA CTN, the study sponsor); NIDA's contracted agents, monitors or auditors; and other agencies such as the Department of Health and Human Services (HHS), the Office for Human Research Protection (OHRP) and the sites' Institutional Review Board may inspect research records for verification of data, compliance with federal guidelines on human participant research, and to assess participant safety.

# 11.22 Reporting to Sponsor

The site principal investigator agrees to submit accurate, complete, legible and timely reports to the Sponsor, as required. These include, but are not limited to, reports of any changes that significantly affect the conduct or outcome of the trial or increase risk to study participants. Adverse Event reporting and Serious Adverse Event reporting will occur as previously described. At the completion of the trial, the Lead Investigator will provide a final report to the Sponsor.

# 11.23 Study Documentation

Study documentation includes all case report forms, data correction forms, workbooks, source documents, monitoring logs and appointment schedules, sponsor-investigator correspondence, and signed protocol and amendments, Ethics Review Committee or Institutional Review Committee correspondence and approved current and previous consent forms and signed participant consent forms.

Source documents include all recordings of observations or notations of clinical activities and all reports and records necessary for the evaluation and reconstruction of the clinical research study. The original recording of an observation should be retained as the source document.

# **11.24** Protocol Deviations, Violations, and Reporting and Management

Any departure from procedures and requirements outlined in the protocol will be classified as either a protocol deviation or protocol violation. The difference between a protocol deviation and violation has to do with the seriousness of the event and the corrective action required. A protocol deviation is considered an action (or inaction) that by itself is not likely to affect the scientific soundness of the investigation or seriously affect the safety, rights, or welfare of a study participant. Protocol violations are departures that may compromise the participant safety, participant rights, inclusion/exclusion criteria or the integrity of study data and could be cause for corrective actions if not rectified or prevented from re-occurrence. Protocol violations will be monitored at each site for (1) significance, (2) frequency, and (3) impact on the study objectives, to ensure that site performance does not compromise the integrity of the trial. The decision about whether a departure from the protocol will be designated as a protocol deviation or a protocol violation will be made by the protocol's Lead Investigator(s) in conjunction with the CCC. The consequences will be specified and participating sites will be informed.

All protocol violations will be recorded in the Electronic Data Capture (EDC) system via the Protocol Violations CRF. Additionally, each site is responsible for tracking and reporting Protocol Violations to their IRB as required. Protocol deviations will be noted by participating sites and reported to their IRBs as required. The CCC and the Data and Statistics Center (DSC) and the Lead Investigator must be contacted immediately if an unqualified/ ineligible participant is randomized into the study.

# 11.25 Safety Monitoring

# 11.25.1 Adverse Events (AEs)

The Lead Investigator (LI) may appoint a Study Clinician (MD, PA, or NP) for this study, who will review or provide consultation for each serious event as needed. These reviews will include an assessment of the severity and causality to the study drug or study procedures. The Study Clinician will also provide advice for decisions to exclude, refer, or withdraw participants as required. In addition, NIDA will assign a Medical Monitor to this protocol to independently review the safety data, present it to the DSMB for periodic review, and provide site principal investigators a Safety Letter when necessary. The medical monitor will determine which safety events require expedited reporting to NIDA, the DSMB, Alkermes, Reckitt Benckiser Pharmaceuticals Inc and regulatory authorities. This will include all suspected adverse reactions that are serious and unexpected. The study staff will be trained to monitor for and report adverse events.

Each of the participating CTPs has established practices for managing medical and psychiatric emergencies, and the study staff will continue to utilize these procedures. Study medical clinicians at each CTP will be responsible for monitoring participants for possible clinical deterioration or other problems, and for implementing appropriate courses of action.

#### **11.25.2** Definitions of Adverse Events and Serious Adverse Events

Standard definitions for adverse events and serious adverse events, their identification, characterization regarding severity and relationship to therapy and processing are described in Appendix A.

#### **11.25.3** Reportable Adverse Events and Serious Adverse Events

#### Adverse Events

For the purpose of this study, the following AE will not require reporting in the data system but will be captured in the source documentation as medically indicated:

• Grade 1 (mild) adverse events

This would typically include mild physical events such as headache, cold, etc., that were considered not reasonably associated with the use of the study drug/intervention.

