#### 6.2 Secondary Outcome Measures

- 1. Adverse events related to study medication across the duration of the study, measured at each clinic visit by appropriately qualified and trained medical personnel;
- 2. Cocaine use will be assessed by a number of outcome measures, including:
  - a. The Treatment Effectiveness Score using urine drug screen results;
  - b. Number of cocaine use days as measured by self-report during the period between randomization and end of treatment;
  - c. Percentage of participants who test free from cocaine use on three successive urine tests;
- 3. Number of days of use of other drugs of abuse as measured by self-report, corroborated by urine drug screen results;
- 4. Severity of cocaine and opioid craving using Visual Analog Craving Scales (VAS);
- 5. Change in depressive symptoms during the period between randomization and end of treatment as measured by the BDI.
- 6. Reduction in drug-related problems between randomization and end of treatment as indicated on the Addiction Severity Index;
- 7. Changes in quality of life between randomization and end of treatment as measured by the World Health Organization Quality of Life BREF instrument;
- 8. Percentage of participants who achieve cocaine abstinence throughout the final two weeks of the evaluation period.
- 9. Percentage of participants who are retained in treatment for the duration of the active treatment phase.
- 10. Number of cocaine use days as measured by self-report during the follow-up period.

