# 8.2.10 Adverse Events (AEs) and Serious Adverse Events (SAEs)

Appropriately qualified and trained medical personnel will assess for any medical or psychiatric side effects, by asking: "How have you been feeling since your last visit?" AEs will be recorded at each visit after consent according to the adverse event reporting definitions and procedures outlined in the protocol. If a reported AE suggests medical or psychological deterioration, it will be brought to the attention of the study medical clinician for further evaluation. SAEs will be medically managed, reported, and followed in accordance with applicable regulatory requirements.

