#### 11.25.4 Known Potential Toxicities of Study Drug/Intervention

Potential adverse events related to buprenorphine+naloxone (BUP, as Suboxone®) include: death, which has been reported among people who abuse BUP in combination with benzodiazepines and other drugs; withdrawal, if BUP is taken while actively taking methadone or various other opioids; increased risk of opioid dependence with continued use of heroin or other opioids; and possible impairment of mental or physical abilities for at least 6 hours after taking BUP.

Common side effects from BUP may include headache, constipation, difficulty sleeping, weakness, sleepiness, nausea, vomiting, sweating, and dizziness. Elevated liver enzyme levels have been reported in participants with hepatitis that are treated with buprenorphine.

As with any new medication, the long-term side effects of BUP are unknown at the present time.

Buprenorphine itself may cause physical dependence. It can also cause intoxication and mild respiratory depression, as evidenced by possible drowsiness and breathing that is slower and shallower.

If the participant attempts to dissolve and inject BUP, he/she may experience opioid withdrawal symptoms, including nausea, diarrhea, hot and cold sweats, hot flashes, muscle cramps, flushing, painful joints, yawning, restlessness, watery eyes, runny nose, chills, gooseflesh, sneezing, abdominal cramps, irritability, backache, tension and jitteriness, depression, sleepiness, shaking or tremor, sensitivity to noise, clammy or damp skin, or other unpleasant effects. Use of other opioids while receiving the BUP tablet could also result in opioid withdrawal symptoms.

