#### Site's Role in Eliciting and Reporting Adverse Events

Appropriately qualified and trained medical personnel will elicit participant reporting of AEs and SAEs at each study visit designated to collect AEs. Adverse events (medical and/or psychiatric) assessment will initiate with participant consent and follow-up will continue through 30 days post last study visit. Medical personnel will obtain as much information as possible about the reported AE/SAE to complete the AE/SAE forms and will consult as warranted.

Standard reporting, within 7 days of the site becoming aware of the event, is required for reportable AEs. Expedited reporting (within 24 hours of their occurrence and/or site's knowledge of the event) is required for reportable SAEs (including death and life-threatening events). Local sites are responsible for reporting SAEs to their IRB, per their IRB's guidelines.

Sites are required to enter reportable AEs and SAEs in the AdvantageEDC system. The AE form is used to capture reportable AEs (as defined in the protocol). Additional information may need to be gathered to evaluate serious adverse events and to complete the appropriate CRFs and the summary. This process may include obtaining hospital discharge reports, medical records, autopsy records or any other type records or information necessary to provide a complete and clear picture of the serious event and events preceding and following the event. If the SAE is not resolved or stable at the time of the initial report or if new information becomes available after the initial report, follow-up information must be submitted as soon as possible.

Reportable adverse events will be followed until resolution, stabilization or study end. Any serious adverse reactions will be followed until resolution or stabilization even beyond the end of the study.

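### The Grade 1 exemption in Protocol 11.25.3 does not settle whether drug-related mild adverse events must be entered, although secondary outcome 1 and the by-arm AE tables have no grade limit

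*Protocol*

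**What the plan says.** Section 11.25.3 of the protocol sets the exemption: "the following AE will not require reporting in the data system but will be captured in the source documentation as medically indicated". One bullet follows, "Grade 1 (mild) adverse events", and then a sentence of explanation: "This would typically include mild physical events such as headache, cold, etc., that were considered not reasonably associated" with the study drug or intervention.

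Two other places carry the exemption into data capture. Appendix A, on the site's role in eliciting and reporting events, states: "The AE form is used to capture reportable AEs (as defined in the protocol". Section 8.2.10 ties recording at visits to the same rules: "AEs will be recorded at each visit after consent according to the adverse event reporting definitions and procedures outlined in the protocol".

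The outcome and analysis sections have no matching limit. The first secondary objective (4.2.2) measures safety by adverse events, without a grade. The first secondary outcome (6.2) is "Adverse events related to study medication across the duration of the study, measured at each clinic visit". Section 10.9 promises that "the number and proportion of participants experiencing at least one incidence of each event will be presented overall and by treatment group", together with a table of total event counts by group.

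Section 11.25.4 lists expected effects: "Common side effects from BUP may include headache, constipation, difficulty sleeping, weakness, sleepiness, nausea, vomiting, sweating, and dizziness".

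**The concern.** Related adverse events are a named secondary outcome, and the trial compares two buprenorphine doses with placebo. If the rule for entering events lets a site leave out related Grade 1 events, part of that outcome is missing from the data before analysis begins. A statistical analysis plan can choose how to tabulate what was entered, but it cannot restore events that never were. Even the source record is conditional, because 11.25.3 asks for it only as medically indicated.

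Consistency is also at stake. With 10 to 12 sites, differing readings of one sentence would make the recorded frequency of mild related events depend partly on the site. The 10.9 tables and the arm differences that the DSMB monitors would then rest on an unstated and uneven severity threshold.

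**Working it through.** No arithmetic applies: the protocol gives no Grade 1 rate and no expected event count by arm. The check sets the sections side by side.

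1. **Scope of the exemption (11.25.3).** The bullet names a severity grade and nothing else. Relatedness appears only in the sentence after it, qualified by the word *typically*, which describes the usual member of a class and does not define its limits. Two readings are open. Under reading A the bullet governs and every Grade 1 event is exempt. Under reading B the sentence limits the bullet and only unrelated Grade 1 events are exempt.

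2. **Where the readings differ.**

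| Event | Entry required, reading A | Entry required, reading B | Within secondary outcome 1 (6.2) |
|---|---|---|---|
| Grade 1, unrelated | No | No | No |
| Grade 1, related | **No** | **Yes** | **Yes** |
| Grade 2 or higher, unrelated | Yes | Yes | No |
| Grade 2 or higher, related | Yes | Yes | Yes |

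The readings part on one row only, and that row lies inside the secondary outcome. The 10.9 tables have no grade limit, so as written they also appear to cover unrelated Grade 1 events, which neither reading requires to be entered.

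3. **Route to the database.** Section 8.2.10 and Appendix A both make recording follow the reporting definitions, so the uncertainty in 11.25.3 passes directly to the AE form.

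4. **Can a site resolve it?** Not easily. Section 11.25.3 uses headache as its example of a mild unrelated event, while 11.25.4 puts headache first among the common buprenorphine effects. Site staff are blinded (7.8.2), so assignment cannot guide them. Appendix A asks trained personnel for an initial judgement of severity and causality, but requires the weekly clinician review only for reportable events. A Grade 1 event treated as exempt therefore keeps only the initial judgement.

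5. **What bounds the loss.** Appendix A ties Grade 1 to discomfort lasting less than 48 hours with no or minimal intervention. Grade 2 starts at mild to moderate limitation of activity, even where little or no intervention is needed. Section 11.25.4 does not grade its list, so the share of those effects that would be Grade 1 is unknown. Injection-site reactions have their own log (8.2.3), with no grade limit stated.

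**The case against.** The strongest reply is that the explanatory sentence in 11.25.3 shows what was meant: unrelated minor events such as colds stay out of the database, and related ones go in. On that view the text needs only a light clarification. The reply is fair as to intent, and the fix below follows it. It does not remove the problem, because a site that applies the bullet literally is also following the protocol.

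A reader might go further and infer that the protocol expressly exempts all drug-related Grade 1 events, that they can never reach the analysis, and that any dose gradient in mild effects would be invisible. The documents do not support this:

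- No sentence says that related events are exempt. That is an inference from a missing condition.
- The rule says that entry is not required; it does not forbid entry.
- Grade 2 and higher events are still tabulated by arm. Tolerability also shows in the dose logs, the End of Medication Form, the injection-site log, ECGs, laboratory tests and vital signs.
- The same wording applies in all three blinded arms, so the threshold does not by itself favour one arm.
- The claim that mild dose-related effects are the likeliest signal is not established. Section 4.1 reports challenge studies in naltrexone-pretreated volunteers in which vital signs and subjective ratings were not significantly affected, although those studies do not rule out mild effects over weeks of dosing.

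It may also be said that a severity threshold for data entry is a legitimate economy, and that entry detail belongs in the CRF completion guidelines. Both are true in general. But this threshold is set in the protocol itself, and it does not match the protocol's own outcome definition.

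**Conclusion.** The point holds as an unresolved conflict within the protocol. Section 11.25.3 leaves open whether related Grade 1 events must be entered, while 6.2 and 10.9 cover them without a grade limit. Related Grade 1 events *need not* reach the database, and practice may differ between sites. It would go too far to say that they are excluded or lost.

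The size cannot be derived: it depends on the Grade 1 rate in each arm and on how each site reads the rule, and the document gives neither. The primary endpoint, SAE reporting, and the capture of Grade 2 and higher events and injection-site reactions are unaffected. The conclusion assumes that no CRF guideline or operations manual, neither of which is at hand, already settles the reading. Even if one does, the protocol wording should agree with it. The change is worth making because it costs little and the omission cannot be repaired at analysis.

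**What to change.** In 11.25.3, make non-relatedness a condition of the exemption: it should apply only to Grade 1 events judged not reasonably associated with study drug/intervention under the causality question in Appendix A. Related Grade 1 events then go on the AE form. Say who answers that question before an event is set aside, since the weekly clinician review now covers only reportable events. Remove headache as the example, or note that it may be related. In 10.9, state that the tables cover all Grade 2 and higher events plus related Grade 1 events, so that readers do not take them as all-grade incidence. Carry the same wording into the CRF guidelines.

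The cost is a wording change and modest extra AE data entry at sites that already ask about events at every visit. Restricting 6.2 and 10.9 to Grade 2 and higher would also remove the contradiction without added entry, but only by narrowing the secondary outcome, so it is the weaker choice. If participants have already been treated under the present wording, the report should give the date of the change, because earlier related Grade 1 events may not be recoverable from source records.
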